#### **4.4. End of Trial Definition**

The end of the trial is defined as the date of the last visit (including the Safety Follow-up Visit) of the last participant in the trial.

The definition of a completed participant is provided in [Section 4.1.4](#).

## 5. TRIAL POPULATION

Men and women, 18 to 65 years of age, inclusive, with a primary diagnosis of panic disorder will be enrolled into the trial.

### 5.1. Inclusion Criteria

Individuals are eligible for participation in this trial only if all of the following criteria apply:

1.	Male and female participants, ages 18-65 years, inclusive, at the time of Screening.
2.	Primary diagnosis of panic disorder based on the DSM-5-TR criteria (present for at least 6 months prior to the Screening Visit) and confirmed by the MINI; additional primary diagnosis of agoraphobia is allowed and secondary diagnosis of GAD and/or SAD is allowed.
3.	Participant has had a minimum of 8 panic attacks, with no week free of panic attacks, in the month prior to the Screening Visit. In the 14 days preceding the Baseline Visit, the participant must have had at least 4 panic attacks and no week free of panic attacks. Note: Participant must complete a minimum of 11 eDiary day entries in the 14 days preceding the Baseline Visit.
4.	Participants with a PDSS total score $\geq 12$ at the Screening and Baseline Visits
5.	Body mass index of 17.5 to 40.0 kg/m  and a total body weight >48 kg at Screening.
6.	A female participant of childbearing potential who is sexually active with a nonsterilized male partner must agree to use a highly effective method of contraception (defined in Section 10.4.1.2 ) from signing of informed consent throughout the duration of the trial until the last dose of IMP and for an additional 33 days after the last dose. A male participant with a pregnant or a nonpregnant partner of childbearing potential must agree to use a condom during treatment and until the last dose of IMP and for an additional 93 days. In addition, male participants should not donate sperm for a minimum of 93 days following last dose of IMP.
7.	Capable of giving signed informed consent, which includes compliance with the requirements and restrictions listed in the ICF and in the trial protocol.
8.	Ability, in the opinion of the investigator, to understand the nature of the trial and comply with protocol requirements, including the prescribed dosage regimens, scheduled visits, laboratory tests, and other trial procedures.

### 5.2. Exclusion Criteria

Individuals are not eligible for participation in this trial if any of the following criteria apply:

Target Disease	
1.	Participants who have a current DSM-5-TR diagnosis of major depressive disorder, dysthymia, bipolar I or II, or other bipolar disorder not specified, posttraumatic stress disorder, obsessive compulsive disorder, eating disorder, phobia (except for agoraphobia), schizophrenia, schizoaffective disorder, other psychotic disorder, delirium, dementia, amnestic disorder, or other cognitive disorder. Participants with a DSM-5-TR personality

	
diagnosis. In addition, participants with any other psychiatric illness, not otherwise specified above, of sufficient severity as to make them inappropriate for the trial are excluded. Per investigator's discretion, the medical monitor should be contacted to discuss individual cases, as needed.
 
 
• Participants with symptoms of depression/dysphoria are allowed if not a primary diagnosis and not requiring medical management.
 
• Participants with a history of alcohol use disorder or substance use disorder within the 6 months prior to Screening will be excluded.
 

2.	
Any newly initiated (within 3 months prior to the Screening Visit) evidence-based psychotherapy, including CBT.
 
 
• Any exposure-based therapy is prohibited throughout the duration of the trial
 

Medical History and Concurrent Diseases	
3.	
Participants with a current history of significant cardiovascular, pulmonary, gastrointestinal, renal, hepatic, metabolic, hematological, immunological, or neurological disease that, in the opinion of the investigator or medical monitor, could compromise either participant safety or the results of the trial.
 
Medical conditions that are minor or well-controlled with non-prohibited concomitant medication(s) may be considered acceptable if the condition does not expose the participant to an undue risk of a significant AE or interfere with the assessments of safety or efficacy during the course of the trial.
 
 
• The medical monitor should be contacted in any instance where the investigator is uncertain regarding the stability of a participant's medical condition(s) or non-prohibited concomitant medication(s) and the potential impact of the condition(s) on trial participation.
 

4.	
Have recently been hospitalized for COVID-19 within 6 months prior to signing the ICF or report a positive test result (ie, using PCR or rapid antigen test) for SARS-CoV-2 within 15 days prior to the Screening Visit.

5.	
Participants who answer "Yes" on the following C-SSRS Suicidal Ideation Items (within the last 6 months)
 
 
• Suicidal Ideation Item 4 (Active Suicidal Ideation with Some Intent to Act, Without Specific Plan) OR
 
• Suicidal Ideation Item 5 (Active Suicidal Ideation with Specific Plan and Intent) OR
 
 
Participants who answer "Yes" on any of the 5 C-SSRS Suicidal Behavior Items (within the last 2 years)
 
 
• Any of the Suicidal Behavior items (actual attempt, interrupted attempt, aborted attempt, preparatory acts, or behavior) OR
 
 
Participants who, in the opinion of the investigator, present a serious risk of suicide.

Physical Examination and Clinical Laboratory Results	
6.	
Positive result for HIV antibody, hepatitis B surface antigen, or hepatitis C antibody at Screening.
 
 
Positive or indeterminate test result for hepatitis C antibody should follow with HCV PCR RNA test. If result is positive, the participant is excluded.
 

7.	
Positive test for alcohol at Screening or Baseline (note: Individuals who test positive for alcohol may be rescreened with approval from the medical monitor).

8.	
Participants with a positive drug screen result at Screening are excluded.
 
 
Participants with a positive urine drug screen resulting from use of any THC containing products, prescription medications (with valid current prescription), or over the counter medications or products who do not meet the criteria for abuse in the investigator's documented opinion may be rescreened after 1 month following consultation and approval by the medical monitor.
 

9.	
Participants with a 12-lead ECG demonstrating any of the following at Screening:
 
 
QTcF >450 msec
 
QRS interval >120 msec
 
Second-degree (Type 2) or third-degree atrioventricular block
 
Clinically significant abnormal heart rhythm (such as atrial fibrillation or flutter, ventricular tachycardia)
 
 
Note: at Screening, eligibility will be based on the average of a centrally read triplicate set of ECGs.
 
At the Baseline Visit, if any of the above criteria are met on the machine read of the ECG, the medical monitor should be consulted to determine whether the participant is eligible for randomization.
 
The medical monitor should be contacted in any instance where the investigator is uncertain regarding the interpretation of ECG results.

10.	
Blood pressure measurements demonstrating any of the following at Screening:
 
 
Systolic blood pressure <math>\geq 140</math> mmHg or diastolic blood pressure <math>\geq 90</math> mmHg 
 
Blood pressure will be measured in triplicate at approximately 1-minute intervals in a supine position after at least 3 minutes of rest. The triplicate measures will be individually recorded and the average of the last 2 measurements will be used to determine eligibility.
 
 
 
Orthostatic hypotension, defined as a decrease of <math>\geq 20</math> mmHg in systolic blood pressure and/or <math>\geq 10</math> mmHg in diastolic blood pressure after at least 2 minutes of standing compared with the average of the resting supine blood pressure measurements
 
Symptomatic postural dizziness (with or without orthostatic hypotension)
 
Heart rate <45 bpm or >100 bpm on vital signs assessment (not ECG)
 

11.	
Participants with any of the following abnormalities in clinical laboratory tests at the Screening Visit, as assessed by the central laboratory and confirmed by a single repeat measurement, if deemed necessary:
 
 
• AST or ALT <math>\geq 2 \times</math> ULN
 
• Total bilirubin <math>\geq 1.5 \times</math> ULN. If Gilbert's syndrome is suspected, total bilirubin <math>>1.5 \times</math> ULN is acceptable if the conjugated or direct bilirubin fraction is <math><20\%</math> of total bilirubin
 
• eGFR <math><60</math> mL/min/1.73 m^2 (as estimated by the CKD-EPI 2021 equation [Levey et al, 2009; Delgado et al, 2022]) and as reported by the central laboratory
 
• TSH <math><</math> LLN
 
• Hemoglobin <math><</math> LLN
 
• WBC count <math><</math> LLN or <math>></math>ULN
 
• Neutrophil count <math><</math> LLN or <math>></math>ULN
 
• Platelet count <math><</math> LLN or <math>></math>ULN
 

12.	
Any other abnormal safety findings unless, based on the investigator's judgment, the findings are not medically significant and would not impact the safety of the participant or the interpretation of the trial results. The medical monitor should be contacted to discuss individual cases, as needed.
 
Tests with abnormal results that are potentially exclusionary should be repeated to ensure reproducibility of the result before excluding a potential participant based on criteria provided in the protocol.

Prior or Concomitant Therapies	
13.	Use of prohibited medications prior to randomization within the required wash-out period or likely to require prohibited concomitant therapy during the trial (see Section 6.7 ).
Other	
14.	Female participants who are breastfeeding or who have a positive pregnancy test result prior to receiving IMP.
15.	
Any condition possibly affecting drug absorption, including bowel resections, bariatric weight loss surgery, or gastrectomy (this does not include gastric banding).
 
Considering or scheduled to undergo any surgical procedure during the trial.

16.	Any other condition that would preclude IMP administration (eg, difficulty swallowing) or trial participation (eg, poor venous access).
17.	Participants who are known to be allergic or hypersensitive to the IMP or any of its components.
18.	
Participants who have participated in any clinical trial within 60 days prior to signing the ICF or who have participated in more than 2 interventional clinical trials within 12 months prior to signing the ICF.
 
Note: Prior participation in an interventional trial and a rollover extension trial with the same IMP within the last 12 months is permitted.

19.	Any participant who, in the opinion of the sponsor, investigator, or medical monitor, should not participate in the trial.

	
 
Employee of the investigator, clinic, or sponsor with direct involvement in the proposed trial or other trials under the direction of the investigator or clinic, as well as family members of the employee or investigator.
 

20.	Refusal to abstain from grapefruit-containing foods or beverages or Seville orange-containing foods or beverages from 7 days prior to dosing through the end of the trial.

Abbreviations: AE=adverse event; ALT=alanine aminotransferase; AST=aspartate aminotransferase; bpm=beats per minute; CBT=cognitive behavioral therapy; COVID-19=coronavirus disease-2019; C-SSRS=Columbia-Suicide Severity Rating Scale; DSM-5-TR=Diagnostic and Statistical Manual of Mental Disorders, Fifth Edition, Text Revision; ECG=electrocardiogram; GAD=generalized anxiety disorder; eGFR=estimated glomerular filtration rate; HCV=hepatitis C virus; HIV=human immunodeficiency virus; ICF=informed consent form; IMP=investigational medicinal product; LLN=lower limit of normal; MINI=Mini International Neuropsychiatric Interview; PCR=polymerase chain reaction; PDSS=Panic Disorder Severity Scale; QRS=Q wave, R wave, S wave; QTcF=QT interval corrected for heart rate using Fridericia's formula; RNA=ribonucleic acid; SAD=social anxiety disorder; SARS-CoV-2=severe acute respiratory syndrome coronavirus-2; THC=tetrahydrocannabinol; TSH=thyroid stimulating hormone; ULN=upper limit of normal; WBC=white blood cell.

### 5.3. Lifestyle Considerations

#### 5.3.1. Meals and Dietary Restrictions

Participants will not be allowed to eat or drink food/food products that are strong/moderate inhibitors or inducers of cytochrome P450 3A4 (including but not limited to grapefruit, grapefruit juice, or grapefruit-related citrus fruits/juices [eg, Seville oranges, pomelos]) from 7 days prior to dosing through the end of trial.

#### 5.3.2. Caffeine, Alcohol, and Tobacco

Participants should adhere to their usual regimen of caffeine and tobacco, if applicable. As the potential for interactions between IMP and alcohol have not yet been evaluated, participants are strongly discouraged from consuming alcohol for the duration of the trial.

#### 5.3.3. Activity

Participants will abstain from strenuous exercise for 48 hours before each blood collection for clinical laboratory tests.

### 5.4. Screen Failures

Screen failures are defined as participants who consent to participate in the clinical trial but are not subsequently randomly assigned to IMP. A minimal set of screen failure information is required to ensure transparent reporting of screen failure participants to meet the Consolidated Standards of Reporting Trials publishing requirements and to respond to queries from health authorities. Minimal information includes demography, screen failure details, and eligibility criteria.

Individuals who do not meet the criteria for participation in this trial (screen failure) at Screening may be rescreened. Individuals may be rescreened once at the discretion of the investigator and after consultation with the sponsor unless screen failure is due to a positive urine drug screen for illicit substances. Rescreened participants should be assigned a new participant number.

## 6. TRIAL INTERVENTION AND CONCOMITANT THERAPY

Trial intervention is defined as any investigational intervention(s), marketed product(s), placebo, or medical device(s) intended to be administered to a trial participant according to the trial protocol.

In this protocol, the trial interventions are referred to as IMPs. An IMP is a pharmaceutical form of an active substance or placebo being tested or used as a reference in a clinical trial, including products already with a marketing authorization but used or assembled (formulated or packaged) in a way different from the authorized form, or when used for an unauthorized indication, or when used to gain further information about the authorized form.

### 6.1. Trial Interventions Administered

A summary of the IMP to be administered during this trial is presented in [Table 4](#).

**Table 4: Investigational Medicinal Products**

IMP	Darigabat 25 mg BID	Placebo BID
Type	Drug	Placebo
Dose Formulation	Tablet	Matching tablet
Unit Dose Strength(s)	5 mg, 7.5 mg, 25 mg	Matching
Dosage Level(s)	
 
5 mg BID (Days 1 to 7)
 
12.5 mg BID (Days 8 to 14)
 
25 mg BID (Day 15 to end of treatment)
 
	0 mg
Route of Administration	Oral	Oral
Sourcing	Provided centrally by Cerevel	
Packaging and Labeling	IMP will be provided in blister packs and/or bottles. Each blister pack or bottle will be labeled as required per country requirement.	

Abbreviations: BID=twice daily; IMP=investigational medicinal product.

### 6.2. Preparation, Handling, Storage, and Accountability

The investigator or designee must confirm appropriate temperature conditions have been maintained during transit (original shipment and/or moving of IMP supply from 1 office or facility to another within the trial site's network) for all IMP received and any discrepancies are reported and resolved before use of the IMP.

Only participants enrolled in the trial may receive IMP and only authorized trial site staff may supply or administer IMP. All IMP must be stored in a secure, environmentally controlled, and monitored (manual or automated) area in accordance with the labeled storage conditions with access limited to the investigator and authorized trial site staff.

The investigator is responsible for IMP accountability, reconciliation, and record maintenance (ie, receipt, reconciliation, and final disposition records).

Further guidance and information for the preparation, handling, storage, accountability, and disposition of unused IMP are provided in the pharmacy manual.

### **6.3. Measures to Minimize Bias: Randomization and Blinding**

#### **6.3.1. Participant Assignment to Treatment**

All participants will be centrally randomized in a 1:1 ratio to 1 of 2 treatment groups (placebo or darigabat 25 mg BID) at the Baseline Visit (Day -1) via an IRT according to a computer-generated randomization scheme. Participants will be sequentially assigned to the next available randomization number and will receive the IMP that corresponds to that randomization number. Once a randomization number has been assigned, it will not be reassigned.

The randomization will be stratified by evidence-based psychotherapy for the treatment of anxiety disorders including panic disorder with 2 strata: receiving evidence-based psychotherapy (initiated >3 months prior to the Screening Visit) or not receiving evidence-based psychotherapy (see [Section 4.1.1](#) for additional details).

#### **6.3.2. Blinding**

During the entire trial, treatment will be blinded such that participants, the blinded sponsor members/designee, raters for clinician-administered scales, the investigator, and other site and trial personnel will not have knowledge of the treatment assignment. Access to the treatment codes or unblinded kit assignments will be restricted to personnel who are responsible for generating and maintaining the randomization code, analyzing the PK blood samples, or unblinded sponsor personnel (for the purposes of packaging/managing IMP supply, supporting IRT, or reporting SAEs or AESI to regulatory agencies). Unblinded personnel are documented in the trial level Blinding Plan.

At the initiation of the trial, investigators and site personnel will be instructed on the method for breaking the blind. In case of an emergency, the investigator has the sole responsibility for determining if unblinding of the treatment assignment for an individual participant is warranted. Participant safety must always be the first consideration in making such a determination. If the investigator decides that unblinding is warranted, the investigator should make every effort to contact the medical monitor before unblinding a participant's treatment assignment unless this could delay emergency treatment of the participant. The medical monitor must be notified within 24 hours after breaking the blind for a trial participant.

Documentation of unblinding should be recorded in the participant's medical record, including the reason for breaking the blind, the date and time the blind was broken, and the names of the personnel involved. Once the blind is broken for a participant, treatment with the IMP may not be reinitiated for that participant.

### **6.4. Trial Intervention Compliance**

Responsible trial personnel will dispense the IMP. Participants will be counseled on the importance of taking the IMP as directed and will be instructed to bring all used and unused IMP to each visit for assessment of accountability and compliance.

Compliance will be assessed by direct questioning and by counting returned tablets. Compliance will be documented in the source documents and the eCRF, including any deviations from the prescribed dosage regimen.

If poor compliance is encountered (eg, multiple missed doses resulting in <80% overall compliance at any point in the trial), discontinuation of the participant from the trial should be considered. Participants who habitually miss visits or habitually attend visits outside of the protocol-defined visit window are also defined as noncompliant and should be considered for discontinuation. The investigator should contact the medical monitor if uncertain whether a participant's lack of compliance merits discontinuation from the trial.

## **6.5. Dose Modification**

No dose modifications are permitted during the trial.

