### **8.3.6. Treatment of Overdose**

An overdose is defined as a known deliberate or accidental administration of investigational drug, to or by a trial participant, at a dose above that which is assigned to that individual participant according to the protocol. Please refer to the darigabat Investigator's Brochure for more detailed information about overdose.

There is no specific antidote for overdose with darigabat. In the event of overdose, treatment should consist of general supportive measures.

In the event of an overdose, the investigator should:

- Contact the medical monitor immediately.

- Closely monitor the participant for any AE/SAE and clinically significant vital sign, ECG, or laboratory abnormalities. Additional safety procedures may need to be performed at the investigator's discretion.
- Document the quantity of the excess dose as well as the duration of the overdose (if multiple time points) in the eCRF.

Decisions regarding dose interruptions or modifications will be made by the investigator in consultation with the medical monitor based on the clinical evaluation of the participant.

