**Table 18: Criteria for Temporarily Withholding IMP in Association With Abnormalities in Liver Test Results**

Baseline ALT Value	ALT Elevation
$< 3 \times \text{ULN}$	

<math>> 8 \times \text{ULN}</math>

<math>> 5 \times \text{ULN}</math> for more than 2 weeks

<math>\geq 3 \times \text{ULN}</math> and (total bilirubin <math>\geq 2 \times \text{ULN}</math> or <math>\text{INR} > 1.5</math>)

<math>\geq 3 \times \text{ULN}</math> with the presence of signs and symptoms consistent with acute hepatitis and/or eosinophilia (<math>\geq 500</math> eosinophils/<math>\mu\text{L}</math>)

Abbreviations: ALT=alanine aminotransferase; IMP=investigational medicinal product; INR=international normalized ratio; ULN=upper limit of normal.

IMP should be withheld pending an investigation ([Table 20](#)) of alternative causes of abnormalities in liver test results ([Table 19](#)). Clinical and laboratory follow-up should continue during the withholding period until the abnormalities in liver test results return to baseline values.

Resumption of IMP can only occur with the express consent of the sponsor and/or their medical designee and only if another cause for the abnormal results is identified and liver tests return to within the normal range.

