4.1.8. Days on IMP

Days on IMP is the number of days from Study Day 1 to the date of last dose of IMP as recorded on the END OF TREATMENT CRF.

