5.11. Primary Efficacy Analysis

5.11.1. Primary Analysis

The primary estimand has the following attributes:

1. Treatments as randomized
2. The population defined by the inclusion/exclusion criteria of the trial as the primary population of interest
3. The proportion of participants who are free of panic attacks during the last two weeks of the Maintenance Treatment as the primary endpoint of interest
4. The population level summary of interest is the estimated odds ratio of freedom from panic attack between treatments and the corresponding 95% confidence intervals (CI)
5. Handling of intercurrent events (ICEs)
 - The treatment policy strategy will be used to handle the ICE of use of concomitant medications during the study for primary analysis of the primary efficacy endpoint, which will include the collected data in the analyses regardless of the use of medications
 - The hypothetical strategy will be used to handle the ICEs of discontinuation from treatment/study participation for primary analysis of the primary efficacy endpoint, which will only include collected data through the discontinuation visit

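### Protocol 6.5 bars all dose modification, but 8.3.6 and 10.6.3 provide for altering or withholding IMP and 7.1/8.3.7 for stopping it; SAP 4.1.8 would count any withheld days as days on IMP

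*Protocol*

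**What the plan says.** **Dosing rules in the protocol**

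- Section 6.5 is a single sentence with no exception or cross-reference: "No dose modifications are permitted during the trial".
- Section 8.3.6 covers overdose. It opens its list of actions with "In the event of an overdose, the investigator should" and closes with "Decisions regarding dose interruptions or modifications will be made by the investigator in consultation with the medical monitor based on the clinical evaluation".
- Section 10.6.3, in the text below Table 18, deals with abnormal liver tests: "IMP should be withheld pending an investigation" of other causes. It then foresees a restart: "Resumption of IMP can only occur with the express consent of the sponsor and/or their medical designee", and only if another cause is found and liver tests are back in the normal range.
- Sections 7.1 and 8.3.7 say that when a QTcF, liver or haematology abnormality meeting the special-interest criteria is confirmed on repeat, study drug is to be discontinued and the early termination visit completed.

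**Recording and analysis**

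- Protocol 6.4 has departures from the dosing regimen documented in the eCRF. Section 8.3.6 has the quantity and duration of an overdose documented there too.
- The SAP computes dosing compliance (4.1.17), summarises it with exposure (5.8), and summarises important protocol deviations and lists all deviations (5.20).
- SAP 4.1.8 defines exposure: "Days on IMP is the number of days from Study Day 1 to the date of last dose of IMP".
- The intercurrent events named in SAP 5.11.1 and 5.12.1.1 are use of concomitant medication and discontinuation. For the latter, SAP 5.11.1 states: "The hypothetical strategy will be used to handle the ICEs of discontinuation from treatment/study participation for primary analysis of the primary efficacy endpoint". SAP 5.12.2.1 uses data from before treatment discontinuation. None of the three mentions interruption.

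**The concern.** A site that must decide whether a participant keeps taking IMP needs one rule. Here the answer depends on which section is opened, and for liver abnormalities the difference is between a pause with a possible restart and a permanent stop. That is a safety-relevant inconsistency whatever the analysis does.

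There is also an analysis consequence. A participant who is paused and restarted has a gap in dosing before the last dose. The exposure definition does not remove that gap, and the estimands do not say whether diary or PDSS data from the gap belong in the analysis. A reader of the exposure table would take the reported days as days on drug.

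**Working it through.** **Step 1. Compare the dosing texts, event by event.**

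| Event | Text A | Text B | Compatible? |
|---|---|---|---|
| Overdose | 6.5: no modification | 8.3.6: interruption or modification decided case by case | No, because 8.3.6 names modification expressly |
| ALT above 8×ULN, confirmed | 10.6.3 / Table 18: withhold, restart possible | 7.1 and 8.3.7 (ALT at or above 5×ULN): discontinue, early termination visit | No |
| ALT at or above 3×ULN with bilirubin at or above 2×ULN, confirmed, another cause found | 10.6.3 / Table 18: withhold, restart possible | 7.1 and 8.3.7: discontinue, with no exception for another cause | No |

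Section 10.6.2 does not settle the last row. It requires permanent discontinuation only when no alternative cause explains the results. Section 8.3.7 refers to 10.6.1 for assessing liver elevations but not to the withholding rule in 10.6.3.

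**Step 2. Check whether the SAP loses sight of an interruption.** It does not. Deviations and overdoses reach the eCRF (Protocol 6.4, 8.3.6), and SAP 4.1.17, 5.8 and 5.20 report compliance and deviations. Two points still depend on resolving Step 1:

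- An altered dose is a deviation under 6.5 but permitted under 8.3.6 or 10.6.3, so its place in the deviation summary is not fixed.
- SAP 4.1.17 divides doses taken by doses expected, without saying whether a withheld dose was expected. Assume 14 withheld days and count each BID administration as one dose. Planned doses are 98 × 2 = 196 and withheld doses 14 × 2 = 28. If withheld doses count as expected, compliance is (196 − 28)/196 = 168/196 = 85.7%. If they do not, it is 168/168 = 100%.

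**Step 3. Size of the exposure error.** The plan's treatment length reproduces: 2 weeks titration + 12 weeks maintenance = 14 weeks, and 14 × 7 = 98 days, matching Day 98 at Visit 6. Take a participant whose last dose is on Day 98 and who had g withheld days before it. SAP 4.1.8 gives 98; days actually on drug are 98 − g.

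| g (assumed) | Days by SAP 4.1.8 | Days on drug | Overstatement as share of planned 98 |
|---|---|---|---|
| 7 | 98 | 91 | 7/98 = 7.1% |
| 14 | 98 | 84 | 14/98 = 14.3% |

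Neither value of g comes from the documents. Section 10.6.3 sets no fixed duration; follow-up during withholding runs until liver results return to baseline values.

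**Step 4. Effect on stated figures.** No number given in the protocol or SAP changes when the sections are reconciled.

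**The case against.** The strongest reply is that the conflict is narrow. Section 6.5 speaks of modification, not interruption, so withholding under 10.6.3 need not breach it. The 8.3.6 sentence applies only after an overdose, and the medical monitor, who must be contacted immediately, shares the decision, which limits variation between sites. For other immediate safety concerns, Section 8 offers only continuing or discontinuing. Participants stay in their randomised arm, and SAP Section 6 declares efficacy exploratory after early closure.

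Most of this stands, and it rules out several stronger readings that a reader might infer:

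- *Investigators have a general power to change the dose for any event.* In 8.3.6 the power covers overdose only and is exercised with the medical monitor.
- *The analysis is unaware of altered dosing.* Deviations and overdoses are recorded and summarised.
- *The SAP asserts that everyone took 25 mg BID from Day 15.* It groups participants by assigned treatment and defines periods by study day. Neither is a statement about dose taken.
- *The treatment comparison is undefined.* With treatments as randomised, data from participants still on study would by default be analysed in the assigned arm. What is missing is a statement that this is intended.
- *An interruption could fill the whole primary window with off-drug days.* Under the individual definition in SAP 4.1.13 the window ends on, and includes, the last dose. (The aggregate wording there is tied to Visit 6 instead.)

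The reply does not remove the clash over modification between 6.5 and 8.3.6. It does not touch the conflict between 10.6.3 and 7.1/8.3.7, which does not involve 6.5. Nor does it change the exposure definition, which counts withheld days.

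**Conclusion.** The point holds in limited form. The protocol contains conflicting written instructions on changing, pausing and stopping IMP, and they must be reconciled. SAP 4.1.8 would overstate days on IMP for any participant withheld and then restarted. The missing statement on interruptions in the estimands is an omission of detail and would not carry the point by itself.

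The number of participants affected is not given. The 7% to 14% range is per affected participant and assumes gaps of 7 to 14 days with a last dose on Day 98. It is an illustration, not an estimate for the trial. Effects on the efficacy conclusions should be small, because analysis is by randomised arm and efficacy is exploratory. The exposure summary is still to be reported, so its definition still matters. No view is taken on which clinical rule is correct.

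**What to change.** 1. **Protocol 6.5, 7.1, 8.3.6, 8.3.7 and 10.6.3.** The sponsor should reconcile these sections so that each event leads to one instruction, with cross-references. If the protocol is no longer being amended after the closure decision, the study report should state which text was applied.
2. **SAP 4.1.8.** Subtract recorded interruption days from days on IMP, or report days on IMP both with and without them. In 4.1.17, state whether withheld doses count as expected.
3. **SAP 5.11.1 and 5.12 (clarification).** State how diary and PDSS data collected during a permitted interruption are handled.

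The cost is wording in both documents and a small change to one derivation. It requires no new assessments, provided the eCRF dosing records give start and stop dates for each gap. The documents say that deviations from the regimen are recorded but do not show the form, so this should be confirmed before database lock.
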